### AADCRC

Those discontinuing peanut for the above reasons will continue with other study procedures (e.g., monthly calls, AE monitoring, SU DBPCFC).

# 7 Other Medications

# 7.1 Concomitant Medications

All subjects may continue their usual medications, including those taken for asthma, allergic rhinitis and atopic dermatitis, during the study. They must, however, be able to discontinue antihistamines prior to skin testing and OFCs. Regular topical steroids use is permitted at the time of skin testing.

### 7.1.1 Protocol-mandated concomitant medications

Participants must have been prescribed epinephrine autoinjectors, see 7.4.

### 7.1.2 Other permitted concomitant medications

Not applicable.

### 7.2 Prophylactic Medications

Participants may receive routine vaccines during the study.

### 7.3 Prohibited Medications

Treatment with biologic therapies will not be allowed during the participation in this study. Other therapeutic interventions for food allergy (e.g. desensitization protocols) will not be allowed. Medications that interfere with treatment of allergic reactions are not allowed (see Exclusion Criteria).

### 7.4 Rescue Medications

Treatment of individual allergic reactions should be with either an H1 and/or H2 antihistamine and/or epinephrine, along with IV fluids, albuterol and steroids as indicated. Subjects and parents will be trained in proper use of an epinephrine autoinjector and will be able to demonstrate proper technique.

# 8 Study Procedures

### 8.1 Enrollment

The research study will be explained in lay terms to each potential research participant. The potential participant will sign an informed consent form before undergoing any study procedures. Once the consent form is signed, the participant will be considered enrolled and will be assigned a unique participant number.

### 8.2 Screening/Baseline Visit

The purpose of the screening period is to confirm eligibility to continue in the study. The procedures involved in the screening/baseline visit will determine if the participant can be randomized to the study intervention or will be characterized as low threshold (LT) peanut allergy or not peanut allergic (NPA). Those who are LT or NPA will participate for mechanistic studies but will not continue to the randomized trial.

### AADCRC

The following procedures, assessments, and laboratory measures (windows for sample collection are detailed in the MOP as applicable) will be conducted, some of which to determine participant eligibility for the randomized trial:

- Physical exam, vital signs, complete medical history
- Spirometry (or peak flow under age 7 or if spirometry not allowed per COVID protocols)
- DBPCFC to peanut per modified PRACTALL (and associated examinations)
- Skin prick test to peanut
- Blood samples (before DBPCFC commences and 2 and 4 hours after starting; not to exceed 5cc/kg on a single day or 9.5ml/kg over any eight-week period per NIH guidelines). A saline lock may be placed to facilitate blood sampling at this and other visits where periodic samples are obtained.
- Quality of life survey, diet questionnaire, demographics
- Urine pregnancy if child bearing potential
- Saliva and stool collection

Screening takes place over 3 days (with one DBPCFC per day for 2 days). Each day is 4-8 hours.

If a participant reacts during the placebo arm of a DBPCFC, the DBPCFC may be repeated once. If a determination of reaction cannot be made due to unwillingness to repeat the DBPCFC or repeated placebo reactions, participation will end and any associated data will not be included in the analyses.

### 8.3 Study Visits or Study Assessments

### Intervention Arm

For those with high threshold peanut allergy randomized to ingestion.

Participants in the intervention arm will receive monthly telephone follow up (unless they have a visit on that month) and reporting of any allergic reactions, including reporting accidental exposure to peanut, and will keep a diary. The diary will be accessed for the following issues: missed dose, ate peanut outside of the study dose, and any reaction, symptoms or illnesses. These will be confirmed/reviewed monthly by telephone, email (printout as source) or in person visit to evaluate that the entries match what the experience is. This will be documented on an eCRF (or email print out) and the clinical team will add any diary entries if needed.

### Visit 1. Initial feeding challenge with subthreshold amount of peanut (visit length 2-3 hours)

- Physical exam, vital signs, medical history
- Spirometry (or peak flow under age 7, or if spirometry not allowed per COVID protocols)
- Open oral food challenge to amount determined by DBPCFC (Section 3.1.3) to confirm tolerance of threshold (if failed, can return for repeated Visit 1 with next lower dose if not already at 1/8 teaspoon).
- Training on measuring amounts for home use
- Provision of diaries and contact instructions

### Escalation Visits (3-8 visits depending upon starting point and progress)

Visits 2 (week 8), 3 (week 16), 4 (week 24), 5 (week 32), 6 (week 40), 7(week 48), 8 (week 56), 9 (week 64) for increasing amounts of peanut (visit length 2-3 hours). These visits stop at week 64 or when 1 Tablespoon (equivalent) is reached.

Attempt to increase daily ingestion by open oral food challenge to next amount higher. Maximum amount is 3 teaspoons/equivalent.

- Physical exam, vital signs, medical history
- Blood samples, Visit 3, week 16 (before feeding challenge commences; not to exceed 5cc/kg on a single day or 9.5ml/kg over any eight-week period per NIH guidelines)
- Spirometry or peak flow (optional under age 7)
- Open oral food challenge to amount determined by DBPCFC (Section 3.1.3) unless at top amount
- Training/review on measuring amounts for home use
- Collection/Provision of diaries and contact instructions
- Saliva and stool collection (visit 3)
- Quality of life survey, diet questionnaire (visit 3)

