### Figure 2. Randomized Intervention Study scheme

### **3.1.3 Intervention Arm Procedures**

Children randomized to the active arm will return for an observed administration of the highest amount of peanut they should tolerate with no or minimal (oral) symptoms based on their baseline DBPCFC. The starting amount of peanut butter will be 1/8th teaspoon [approximately 140 mg peanut protein] if they reacted at 443 mg cumulative dose on DBPCFC, ¼ teaspoon [approximately 280 mg peanut protein], if they reacted at 1043 mg cumulative dose on DBPCFC, 3/8 teaspoon [approximately 430 mg peanut protein] for a reaction at 2043 mg cumulative dose) or 1 teaspoon [approximately 1140 mg] for a reaction at 5043 mg cumulative dose. To continue on daily peanut, the 1/8th teaspoon supervised feeding post food challenge must be tolerated. Study participants/families will be given detailed instructions

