### AADCRC

specifying the types and amounts of the commercial foods allowed for home ingestion. They also will be required to strictly avoid the food allergen other than the amount under the study. They will return every 8 weeks to attempt a supervised feeding of the next higher amount, as shown in **Figure 2**. If successfully consumed, they will continue the one step higher amount daily. When participants have exceeded 3/8 teaspoon of peanut butter, alternative forms (Bamba™, candies) can be substituted but such substitutions will be performed as observed feedings. (Table available in the MOP.) If subjects have symptoms at 1/8 teaspoon peanut butter during the study, they will be permitted to trial 1/16th teaspoon under observed feeding, but this will be the lowest amount allowed in the study.

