If the subject experiences *mild symptoms*, defined as:

- Skin non-perioral hives/swelling, skin flushing or pruritus
- Respiratory rhinorrhea/sneezing, nasal congestion, occasional cough, throat discomfort
- GI abdominal pain that is more than mild transient/minor episode of vomit

The action should be either to repeat the daily amount at home, or a reduced amount, or to have the subject return to the site for a repeat of the ingested amount or to trial a step lower amount (at the physician's discretion). If the amount is tolerated, then the subject will continue on that amount until the next scheduled visit. If the ingestion again causes mild symptoms, then the subject may return to the site to trial a lower amount, as possible.

If the subject experiences *moderate symptoms*, defined as:

- Skin systemic hives/swelling
- o Respiratory throat tightness without hoarseness, persistent cough, wheezing without dyspnea
- GI persistent moderate abdominal pain/cramping/nausea, increased vomiting

The action should be to have the subject return to trial a lower amount, as possible and with physician discretion. If this amount is tolerated, it will be continued as the daily home ingestion amount until the next scheduled visit. If the amount is not tolerated, then a discussion with the Study PI or Co-PI will ensue to make a decision about whether to continue the subject on active ingestion in the study.

If the subject experiences *severe symptoms*, defined as:

- Respiratory laryngeal edema, throat tightness with hoarseness, wheezing with dyspnea
- GI significant severe abdominal pain/cramping/repetitive vomiting
- Neurological change in mental status
- Circulatory hypotension

The action should be to treat the subject, and at the physician's discretion either 1) have them return to the site for trial of a 2 step lower (at least) amount under observation or 2) discontinue them from the active arm. If the subject tolerates the reduction, then they will remain on that amount until the next scheduled visit. A discussion with the Study PI or Co-PI may ensue to make a decision about whether to continue the subject on active treatment in the study.

For a completed ingestion visit with no symptoms, subjects should be observed for 30 minutes. For mild symptoms, subjects should have a 1-2 hours post ingestion observation period. For moderate to severe

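### Protocol Section 8.3 states the Visits 2-9 feeding amount in two conflicting ways, and Section 8.4 does not settle it for a child who was stepped down

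*Protocol*

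**What the plan says.** **Protocol 8.3, Escalation Visits (Visits 2-9).** The lead sentence is "Attempt to increase daily ingestion by open oral food challenge to next amount higher", with a maximum of 3 teaspoons. The procedure list beneath it says "Open oral food challenge to amount determined by DBPCFC (Section 3.1.3) unless at top amount".

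**Protocol 8.3, Visit 1.** The corresponding bullet is "Open oral food challenge to amount determined by DBPCFC (Section 3.1.3) to confirm tolerance of threshold". Here the amount is the starting dose.

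**Protocol 3.1.3.** The only amounts this section ties to the DBPCFC are four starting amounts by baseline reaction dose:
- one eighth of a "teaspoon [approximately 140 mg peanut protein] if they reacted at 443 mg cumulative dose on DBPCFC"
- one quarter of a "teaspoon [approximately 280 mg peanut protein], if they reacted at 1043 mg cumulative dose on DBPCFC"
- 3/8 teaspoon (about 430 mg) for a reaction at 2043 mg
- "1 teaspoon [approximately 1140 mg] for a reaction at 5043 mg cumulative dose"

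Later in the same section comes the progression rule: "They will return every 8 weeks to attempt a supervised feeding of the next higher amount". Protocol 3.1.2, the Visits 2-9 column of Table 2 and SAP 3.1.1 also describe these visits as attempts at a larger amount.

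**Protocol 8.4.** After severe symptoms at home, one of the physician's two options is a "trial of a 2 step lower (at least) amount under observation"; the other is discontinuation. A reduced amount that is tolerated is kept until the following planned visit. Section 8.4 does not say what is fed at that visit.

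**The concern.** The feeding amount at Visits 2-9 is the operative dosing instruction of the intervention arm, and one subsection states it in two ways that usually give different amounts. Staff who work from a visit's procedure list would meet the bullet, not the lead sentence. Under Protocol 15.1 any departure from the protocol is a deviation, so whichever amount is fed, one of the two sentences is contradicted.

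The child who has been stepped down matters most. Section 8.4 is silent on the next planned visit, so the reader goes back to 8.3 and finds two answers. For some of these children the bullet's answer is the larger one, shortly after a reaction.

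**Working it through.** **Inputs.** The ladder (Protocol Synopsis, Treatment Description; SAP 3.1.1) has nine rungs: 1/8, 1/4, 3/8, 1/2, 3/4, 1, 1.5, 2 and 3 tsp. The starting amounts are those in Protocol 3.1.3. Visits are 8 weeks apart, and the desensitization DBPCFC comes 8 weeks after 1 tablespoon (3 tsp) is reached. Protein is taken at about 1140 mg per teaspoon (3.1.3).

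**Step 1. Reproduce the protocol's schedule with the lead sentence.** Visits needed = 9 − position of the starting rung. DBPCFC week = 8 × visits + 8.

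| Baseline reaction dose | Start (position) | Visits to 3 tsp | DBPCFC week |
|---|---|---|---|
| 443 mg | 1/8 tsp (1) | 9 − 1 = 8 | 64 + 8 = 72 |
| 1043 mg | 1/4 tsp (2) | 9 − 2 = 7 | 56 + 8 = 64 |
| 2043 mg | 3/8 tsp (3) | 9 − 3 = 6 | 48 + 8 = 56 |
| 5043 mg | 1 tsp (6) | 9 − 6 = 3 | 24 + 8 = 32 |

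This gives 3 to 8 visits, as in the 8.3 subsection title, and weeks 32, 56, 64 and 72, as in Table 2.

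**Step 2. Compare the two instructions.** Let s be the starting rung and c the current rung. The lead sentence gives c + 1. The bullet, read as at Visit 1, gives s. They agree only if c = s − 1. Otherwise:
- c = s (for example, Visit 2 after an uneventful start): the bullet offers no increase.
- c above s: the bullet feeds c − s rungs below the daily amount. A child who started at 1/8 tsp and now takes 3/4 tsp would be fed (1/8) ÷ (3/4) = 1/6 of the daily amount.
- c = s − d with d of 2 or more: the bullet feeds d rungs above the current amount, against one rung under the lead sentence.

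**Step 3. Size after a net two-rung reduction below the start (d = 2).**

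| Baseline reaction dose | Current | Lead sentence | Bullet | Bullet ÷ current |
|---|---|---|---|---|
| 5043 mg | 1/2 tsp (570 mg) | 3/4 tsp (855 mg) | 1 tsp (1140 mg) | 2 |
| 2043 mg | 1/8 tsp (142.5 mg) | 1/4 tsp (285 mg) | 3/8 tsp (427.5 mg) | 3 |
| 1043 mg | 1/16 tsp (71.25 mg) | 1/8 tsp (142.5 mg) | 1/4 tsp (285 mg) | 4 |
| 443 mg | not possible | – | – | – |

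The 1043 mg row counts 1/16 tsp as a rung. The ladder itself starts at 1/8 tsp; 3.1.3 and 8.4 allow 1/16 tsp only as an exception for a child who has symptoms at, or cannot take, 1/8 tsp. The 443 mg row is empty because those children start at 1/8 tsp and can drop only to 1/16 tsp.

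**Step 4. Sample size.** The power statement (36 per group, 46% versus 12.25%) uses no feeding amount, so the wording does not change it.

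**The case against.** The strongest reply is that the bullet sets no rival dose. It points to Section 3.1.3, which also contains the eight-weekly progression rule. Its closing exception makes sense only for an escalating amount, because the highest starting amount is 1 tsp and the top is 3 tsp. The subsection's title, its lead sentence, Protocol 3.1.2, Table 2 and SAP 3.1.1 all describe escalation, and Step 1 confirms that the schedule was built on it. The trial has one site, and the Manual of Procedures, which might settle the point, is not among the documents. All of this stands, and it makes carried-over Visit 1 wording the likeliest explanation.

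Three stronger readings are tempting but not supported:
- **A fixed-dose trial.** A reader might infer that escalation stops, no child reaches 1 tablespoon and every intervention DBPCFC falls at week 72. That would require staff to set aside the lead sentence and every other description of these visits, for every child.
- **A general risk of multi-rung jumps.** The jump needs a net reduction of at least two rungs below the starting amount, a decision to continue ingestion (8.4 also allows discontinuation), and staff following the bullet. A two-rung reduction that leaves the child at or above the start does not produce it.
- **A return to the reaction-causing amount that is peculiar to the bullet.** After a one-rung reduction, the lead sentence also leads back to that amount.

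The reply does not remove the conflicting sentence from the procedure list, and it does not supply the instruction missing from 8.4.

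**Conclusion.** Section 8.3 is internally inconsistent about the feeding at Visits 2-9. This is an inconsistency of wording, not a design choice. The weight of the documents favours escalation, and a trial-wide failure to escalate is unlikely.

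The practical exposure is limited to staff working from the bullet. A child above the starting amount would then be fed less than the daily amount. A child who started above 1/8 tsp, was stepped down a net two or more rungs below the start and stayed on ingestion would be fed two or more rungs above the current amount. At a two-rung reduction that is 2 times the current amount in the 5043 mg stratum and 3 times in the 2043 mg stratum. The 4-times figure in the 1043 mg stratum holds only if 1/16 tsp is treated as a rung.

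These sizes assume the bullet carries its Visit 1 meaning and that peanut butter supplies about 1140 mg of protein per teaspoon; the multiples themselves depend only on the spoon sizes. The documents do not show how many children would be affected. The point merits correction because it concerns operative dosing text and the correction is small.

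**What to change.** The investigators should reconcile the procedure bullet and the lead sentence in Protocol 8.3 with 3.1.2, 3.1.3, 8.4 and SAP 3.1.1, so that Visits 2-9 carry a single feeding instruction. That instruction should state explicitly what applies at the next planned visit to a child who was stepped down under 8.4, including a child on 1/16 tsp. Which amount or rule is intended is for the investigators to decide; none is proposed here.

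The cost is a change to one bullet, a clarifying sentence in 8.3 or 8.4, and any site worksheet that repeats the bullet. No added visits, participants or analyses are needed.

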# Desensitization DBPCFC visit, (week 72 or 8 weeks after reaching 1 Tablespoon or equivalent. Visit length 4-8 hours each of 2 days.

- Physical exam, vital signs, medical history
- Blood samples (before feeding challenge commences and 2 and 4 hours after starting; not to exceed 5cc/kg on a single day or 9.5ml/kg over any eight-week period per NIH guidelines)
- Spirometry or peak flow (optional under age 7)
- DBPCFC to peanut per modified PRACTALL (and associated examinations)
- Skin prick test to peanut
- Quality of life survey, diet questionnaire
- Urine pregnancy if child bearing potential
- Saliva and stool collection

This is the end of study visit for those not tolerating the DBPCFC and they will transfer to clinical management off of the study. Those tolerating the DBPCFC will proceed to the SU visit.

# Additional visits for evaluation of Sustained Unresponsiveness in Intervention Arm

Sustained unresponsiveness visit for DBPCFC following 16 weeks of "ad lib" peanut (no upper limit but at least 2 Tablespoons peanut butter or equivalent per week) and then 8 weeks peanut avoidance following the desensitization DBPCFC (visit length 4-8 hours each of 2 days).

If the desensitization DBPCFC is passed, the subject will be instructed to incorporate peanut into the diet for 16 weeks. If this is tolerated, peanut will then be avoided for 8 weeks at which time the following procedure will be performed:

- Physical exam, vital signs, medical history
- Blood samples (before feeding challenge commences and 2 and 4 hours after starting ; not to exceed 5cc/kg on a single day or 9.5ml/kg over any eight-week period per NIH guidelines)
- Spirometry (or peak flow under age 7, or if spirometry not allowed per COVID protocols)
- DBPCFC to peanut per modified PRACTALL (and associated examinations)
- Skin Prick Test to peanut
- Saliva and stool collection
- Urine pregnancy if child bearing potential
- Diet questionnaire, Quality of life survey

If this DBPCFC is tolerated, the subject will eat peanut "ad lib" but with at least one weekly serving recommended (serving is about 2 Tablespoons peanut butter or equivalent). If this DBPCFC is not tolerated, the subject will undertake clinical management off of the study.

### Control Arm

Participants in the control arm will receive monthly telephone follow up and reporting of any allergic reactions, including reporting accidental exposure to peanut, and will keep a diary. The diary will be accessed for the following issues: ate peanut, and any reaction, symptoms or illnesses. These will be confirmed/reviewed monthly by telephone, email (printout as source) or in person visit to evaluate that the entries match what the experience is. This will be documented on an eCRF (or email print out) and the clinical team will add any diary entries if needed. They will have a visit 16 weeks following the initial DBPCFC for review of avoidance instructions and collection of a blood sample, saliva and stool for mechanistic studies, and QoL and diet questionnaires. The control arm subjects will undergo a DBPCFC and procedures listed under desensitization DBPCFC (above) are performed at a time determined by a surveillance algorithm (see Section 13.3). Control arm participants do not require follow up for SU. Those unable to tolerate the DBPCFC will pursue clinical management off of the study, those who tolerate the full feeding may add peanut to the diet "ad lib" but with at least one weekly serving recommended and pursue clinical care off of the study.

### 8.4 Unscheduled Visits

If disease activity increases or other concerns arise between regularly scheduled visits, participants will be instructed to contact study personnel and may be asked to return to the study site for an "unscheduled" visit. If the participant becomes/is unable to ingest at least 1/8 teaspoon of peanut butter, they will undergo a supervised feeding of 1/16th teaspoon, which is the lowest amount permitted and may become the daily amount if tolerated. If the participant cannot ingest 1/16th teaspoon of peanut butter they will be considered a treatment failure and will stop any daily ingestion, but will undergo the endpoint DBPCFCs at 72 weeks.

The following circumstances may lead to unscheduled visits (active arm):

1. Concern regarding peanut ingestion triggering increased chronic symptoms (e.g., increased eczema, gastrointestinal symptoms).

Procedures (1-8 hour visit):

- Physical exam, vital signs, medical history
- Spirometry (or peak flow under age 7, or if spirometry not allowed per COVID protocols)
- DBPCFC to the amount being ingested on a daily basis, or supervised open feeding of the amount ingested on a daily basis, or supervised feeding of a lower amount, as deemed necessary for full evaluation

The PI/Investigator and family will determine whether to continue daily ingestion, reduce the daily amount, or follow off intervention, and/or refer for additional medical evaluation (i.e., endoscopy).

2. Concern regarding acute symptoms from home ingestion.

Participants will be instructed to contact the PI/Investigator/study team for acute allergic symptoms (with the exception of oral pruritus, mild transient abdominal discomfort, or perioral redness/hives). The investigator will determine the best course of action, with possible actions being the following:

- 1. Continue with daily home dosing
- 2. Return for an observed ingestion of the same amount
- 3. Return for an observed ingestion of a step lower amount.
- 4. Discontinuation of ingestion

The following process algorithm will be applied regarding symptoms associated with the daily ingestion.

If the subject only experiences oral/pharyngeal pruritus, or perioral redness/hives, or mild transient abdominal discomfort, the daily ingestion may continue. Instructions about eating peanut with meals will be reviewed. If the symptoms are bothersome or persistent, procedures per #1 above (chronic symptoms) will be followed.

If the subject experiences *mild symptoms*, defined as:

- Skin non-perioral hives/swelling, skin flushing or pruritus
- Respiratory rhinorrhea/sneezing, nasal congestion, occasional cough, throat discomfort
- GI abdominal pain that is more than mild transient/minor episode of vomit

The action should be either to repeat the daily amount at home, or a reduced amount, or to have the subject return to the site for a repeat of the ingested amount or to trial a step lower amount (at the physician's discretion). If the amount is tolerated, then the subject will continue on that amount until the next scheduled visit. If the ingestion again causes mild symptoms, then the subject may return to the site to trial a lower amount, as possible.

If the subject experiences *moderate symptoms*, defined as:

- Skin systemic hives/swelling
- o Respiratory throat tightness without hoarseness, persistent cough, wheezing without dyspnea
- GI persistent moderate abdominal pain/cramping/nausea, increased vomiting

The action should be to have the subject return to trial a lower amount, as possible and with physician discretion. If this amount is tolerated, it will be continued as the daily home ingestion amount until the next scheduled visit. If the amount is not tolerated, then a discussion with the Study PI or Co-PI will ensue to make a decision about whether to continue the subject on active ingestion in the study.

If the subject experiences *severe symptoms*, defined as:

- Respiratory laryngeal edema, throat tightness with hoarseness, wheezing with dyspnea
- GI significant severe abdominal pain/cramping/repetitive vomiting
- Neurological change in mental status
- Circulatory hypotension

The action should be to treat the subject, and at the physician's discretion either 1) have them return to the site for trial of a 2 step lower (at least) amount under observation or 2) discontinue them from the active arm. If the subject tolerates the reduction, then they will remain on that amount until the next scheduled visit. A discussion with the Study PI or Co-PI may ensue to make a decision about whether to continue the subject on active treatment in the study.

For a completed ingestion visit with no symptoms, subjects should be observed for 30 minutes. For mild symptoms, subjects should have a 1-2 hours post ingestion observation period. For moderate to severe

symptoms, the observation period should be at least 4 hours and up to 24 hours based on symptoms and treatment regimen needed to stabilize.

3. Excessive days without ingestion of peanut.

Participants will be instructed to skip days ingesting peanut for illness. However, if more than 5 consecutive days are missed, at the discretion of the PI, a visit for observed feeding may be undertaken versus allowing continuation at home.

4. Early withdrawal.

If the PI/Co-I or participant wishes to discontinue participation in the study, they will be asked to attend an early withdrawal visit for review of their diet, collection of diaries, blood, stool and saliva for mechanistic studies and completion of a QOL survey and diet questionnaire.

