### **11.4** Follow-up after Early Study Withdrawal

See section 8.4.

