6.5.2.3 Quality of life

Changes in quality of life over the study as measured by The Food Allergy Quality of Life-Parental Burden²³ will be compared between randomization groups and analyzed using linear mixed effects models for data collected at baseline, week 16, and the desensitization DBPCFC visit. The analysis will include a random subject effect and the fixed effect of randomization assignment, continuous time, and their interaction. Spline models may be considered if the curves exhibit non-linear trends. If the MAR assumption for linear mixed models is not plausible, pattern-mixture modeling will be used. The All Available Data population will be used for this analysis.

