Immunocap Assay: Changes in serum component proteins measured through ImmunoCAP assay will be compared between randomization groups using linear mixed effects models for data collected at baseline, week 16 and the desensitization double-blind, placebo-controlled food challenge visit. The analysis will include a random subject effect and the fixed effect of randomization assignment, time, interaction between randomization assignment and time, and age. Spline models may be considered if the curves exhibit non-linear trends. Values below the limit of detection (LOD) will be imputed as X/sqrt(x)). The linear mixed effects model has the advantage that the estimation of the model parameters will be unbiased even in the presence of missing outcomes, assuming that the missing values depend only on the observed values (missing at random). If the missing at random assumption is not plausible, pattern-mixture modeling (which stratifies subjects by their pattern of missing data) will be used.

Cell population frequency: Quantile-linear mixed effects models will be used for the frequency of %CD63+ basophil, peanut-specific Th2 cells and T cells.

BBEA Assay: The bead-based epitope assay (BBEA) protocol will be used to obtain peanut specific of 64 15-mer epitopes derived from key peanut allergens—34 from Ara h 1, 16 from Ara h 2, and 14 from Ara h. All data processing, quality control, and analyses will be performed in R (version 4.3.3; R Foundation, Vienna, Austria). Binding scores for each epitope in the IgE and IgG4 assays will be obtained via *bbeaR*. Plate effect will be assessed using Principal Variation Component Analysis along with age strata, randomization assignment, visit, the interaction between randomization assignment and visit, and participant. If Plate effect is considered to be large, ie >10% contribution to the variance, Plate will be included as a factor in all analysis. Linear mixed effects models will be fitted by using the *limma* framework– for high dimensional omic data.

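### Quality-of-life and serum values collected at the early-withdrawal visit are not among the data the SAP models use, and the protocol should say the visit covers both arms (minor)

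*Protocol*

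**What the plan says.** **What is collected.** Item 4 of protocol 8.4 opens "If the PI/Co-I or participant wishes to discontinue participation in the study" and provides that "they will be asked to attend an early withdrawal visit for review of their diet, collection of diaries, blood, stool and saliva". It adds "completion of a QOL survey and diet questionnaire".

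**What is modelled.** SAP 6.5.2.3 analyses quality of life with "linear mixed effects models for data collected at baseline, week 16, and the desensitization DBPCFC visit". The model has a random subject effect, with arm, continuous time and their interaction as fixed effects. The Immunocap Assay paragraph of the SAP addendum also uses a linear mixed model, "for data collected at baseline, week 16 and the desensitization double-blind, placebo-controlled food challenge visit". Neither list includes the early-withdrawal visit. Protocol 13.4.4 describes the quality-of-life comparison as running over the study and lists no visits, so the restriction comes from the SAP.

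**To whom the visit applies.** The list that contains item 4 is introduced with "The following circumstances may lead to unscheduled visits (active arm". Protocol 11.4, on follow-up after early withdrawal, reads only "See section 8.4". For controls, protocol 8.3 provides monthly calls, one interim visit ("They will have a visit 16 weeks following the initial DBPCFC for review of avoidance instructions") and the repeat DBPCFC. It mentions no exit visit.

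**The concern.** Quality of life is a secondary objective. The instrument is a parent-burden questionnaire, and families know their assignment. After week 16 the next modelled score is at the desensitization visit, which Table 2 of the protocol places between weeks 32 and 72 and which has a window of up to six months. If a family leaves in between because of reactions or burden, the change may appear only in the exit score.

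A mixed model is valid under MAR given the data it is fed. Without the exit score, a leaver's later course is in effect projected from the baseline and week-16 scores along the trend of those who stayed. With it, the model conditions on the observation closest to the decision to leave. The score is collected anyway, and a continuous-time model can take it at whatever week it falls.

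The question of arm belongs with this. If exit scores entered the model but had been gathered mainly from consumers, one imbalance would replace another.

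**Working it through.** **1. Text check.** The exit visit yields a quality-of-life score and blood (protocol 8.4). The modelled time points are baseline, week 16 and the desensitization visit (SAP 6.5.2.3 and addendum). The exit visit is none of these, and nothing in the SAP says how its data are to be used.

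**2. How many children.** The plan states no study-withdrawal rate. The 20% in protocol 13.7 is consumers discontinuing study treatment. The plan's own attenuation uses it that way: 0.55 × 0.80 + 0.10 × 0.20 = 0.46, which reproduces the stated 46%. Those children are counted at the control rate, not as missing. As an assumption, if 5% to 20% left the study before the desensitization visit, that is 36 × 0.05 = 1.8 to 36 × 0.20 = 7.2 children per arm, or 3.6 to 14.4 of 72.

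**3. Size of the effect (all inputs assumed).**
- 36 children per arm. Between-child SD is 0.8 and residual SD 0.6, so the total SD is √(0.64 + 0.36) = 1.
- Consumers who stay gain 0.5 SD linearly by week 72. Controls do not change.
- 10% of controls leave, and 10% or 20% of consumers leave. All exits are at week 32.
- Leaving consumers follow the stayers' path at week 16, are 0.5 or 1 SD below **baseline** at exit, and remain there to week 72.

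True arm difference at week 72:
- 10% leave, 0.5 SD below: 0.9 × 0.5 − 0.1 × 0.5 = 0.40
- 20% leave, 0.5 SD below: 0.8 × 0.5 − 0.2 × 0.5 = 0.30
- 20% leave, 1 SD below: 0.8 × 0.5 − 0.2 × 1.0 = 0.20

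The expected estimate from a random-intercept model is β = (Σ n XᵀV⁻¹X)⁻¹ Σ n XᵀV⁻¹μ. Here X holds intercept, arm, time and arm × time, V = 0.64 J + 0.36 I, and the sum runs over stayers and leavers in each arm. The effect can be read as the difference in change (72 × the interaction slope) or as the arm difference at week 72.

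| Case | True | SAP visits only | With exit: change | With exit: week 72 |
|---|---|---|---|---|
| 10%, 0.5 SD | 0.40 | 0.50 | 0.47 | 0.46 |
| 20%, 0.5 SD | 0.30 | 0.50 | 0.44 | 0.41 |
| 20%, 1 SD | 0.20 | 0.50 | 0.40 | 0.35 |

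Simulated trials under these assumptions agree. Without and with the exit score they gave 0.51/0.48 in the first case, 0.50/0.44 to 0.51/0.42 in the second, and 0.50/0.39 to 0.49/0.34 in the third. Much of the spread within a case comes from which of the two readings is used. The shift is 0.51 − 0.48 = 0.03 at the least and 0.49 − 0.34 = 0.15 at the most. In the second case the bias is 0.50 − 0.30 = 0.20, and 0.06 to 0.09 of it is removed.

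**4. Against sampling error.** The SD of the estimate is about 0.20 for the difference in change and about 0.24 at week 72. Every shift above is smaller than one such SD.

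**5. If the deterioration does not last.** If leavers return to baseline by week 72, the true difference at 20% leaving is 0.8 × 0.5 + 0.2 × 0 = 0.40, and the bias without the exit score is 0.10. Adding the score then gives 0.41 to 0.44 when leavers were 0.5 SD below at exit, close to the truth. When they were 1 SD below it gives about 0.34 to 0.40, which can overshoot. The gain is therefore general, not guaranteed.

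**The case against.** **Children who stop peanut are mostly still followed.** Protocol 6.5 keeps those who discontinue ingestion in the other study procedures, and 8.4 still brings treatment failures to the endpoint DBPCFC, where quality of life is collected. This stands: the point concerns only children who leave the study, and a 20% exit rate may overstate their number.

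**The SAP has a fallback.** If MAR is implausible, pattern-mixture modelling is to be used in both analyses. This also stands, but it does not replace the exit score, which is an observed value that bears on whether MAR is plausible.

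**The stakes are low.** The exit visit includes no DBPCFC, so it adds nothing to the primary endpoint. SAP 6.6 treats secondary p-values as descriptive. Both are correct and limit the priority, although a descriptive estimate can still be biased.

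**Stronger readings to avoid.** A reader might infer from the lead-in that only active-arm children have an exit visit, and so that withdrawals are followed differently by arm. The documents do not establish that. The sentence in item 4 speaks of any participant, 11.4 points to 8.4 without limiting the arm, and Table 2 omits unscheduled visits and cannot settle it. Adverse-event follow-up after withdrawal (protocol 12.4.1) is the same in both arms. This is an ambiguity that could lead to unequal collection, not a stated difference. A reader might also infer that the exit score is to be discarded. Neither document says so; the score is simply absent from the SAP's list of visits.

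**Conclusion.** The point holds as a minor one. Followed as written, the SAP leaves out a quality-of-life score and serum values that the protocol collects at withdrawal, which weakens the MAR assumption behind two mixed models. Under the assumed inputs, including the exit score moves the quality-of-life estimate by about 0.03 to 0.15 SD, generally towards the truth, and removes only part of the bias. The sampling SD is about 0.2 to 0.25.

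These sizes rest on an assumed withdrawal rate, an assumed deterioration and its assumed persistence; the documents supply none of the three. No size was worked out for the ImmunoCAP model. The effect is confined to secondary and mechanistic endpoints and to children who leave the study. The arm question is a matter of clarification only.

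**What to change.** 1. **SAP 6.5.2.3.** Add the early-withdrawal visit to the data used, with the score entered at its actual week. The model already has continuous time, so the method does not change.
2. **SAP addendum, Immunocap Assay.** Include early-withdrawal serum values at their actual time. The addendum says time without saying continuous, so state how time is coded; if it is coded by visit, the exit values need an explicit place.
3. **Protocol 8.3 (Control Arm), 8.4 and 11.4.** State that the early-withdrawal visit applies to both arms, for example by moving item 4 out of the active-arm list.

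The cost is wording. The SAP allows revision before data lock, and the visit and its procedures already exist. At most, a few withdrawing controls attend a visit that the protocol may already intend for them.
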